The concept of the glycemic index has been expanded over the years, giving rise to mathematical products such as the glycemic load (GL), which is defined as the quantity and quality of carbohydrates consumed and estimates the total glycemic effect of the diet, for its obtaining it is necessary to multiply the amount of CHO contained in the food ingested by the GI value ($GL = GI \times \text{available carbohydrates}$).

The increase to the glycemic load is associated with an unfavorable physiological response, mainly for people living with diabetes, since blood glucose and insulin values rise sharply. Foods with $GL \leq 10$ are considered low GL and foods with $GL \geq 20$ are considered high GL.

OBJECTIVES

General objective

To evaluate the *in vivo* bioavailability of bioactive compounds from a *H. sabdariffa* beverage and their immunomodulatory potential against moderate inflammation caused by SARS-CoV2 as well as enzymatic inhibition of α -amylase and α -glucosidase enzymes *in vitro*.

Specific objectives

1. To perform HPLC-DAD-MS characterization of a *Hibiscus sabdariffa* hibiscus-based beverage.
2. To perform an acute single-blind clinical trial, administering a hibiscus drink to normal-weight adults.
3. To evaluate the bioavailability of organic acids and phenolic compounds in urine and plasma samples present in the *H. sabdariffa* beverage.
4. To evaluate the immunomodulatory potential of the metabolites identified as bioavailable in plasma samples.
5. To evaluate the enzymatic inhibition of α -amylase and α -glucosidase exerted by the digested, placebo and treatment beverages.
6. To evaluate the *in vivo* GR and IR of the placebo beverage and treatment beverage.

. GENERAL METHODOLOGY

First Stage

Obtaining hibiscus-based beverage and placebo.

The hibiscus-based beverages (H.sabdariffa) and placebo were obtained from the reformulated company NUTRIYÉ SAPI de CV, located in the city of Guadalajara, Jalisco, Mexico.

Participants.

Twelve normo-weight volunteer participants without any medical condition were included. The invitation to participate was made through ITESO's communications office, as well as through announcements in social networks. They were selected according to the following criteria:

Within the inclusion criteria to be considered are those mentioned in Table 4.2.

Table 4.2. Non-inclusion and inclusion criteria for volunteer selection.

Inclusion criteria		Non-inclusion criteria	

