Normolipidemia	Total cholesterol (plasma) < 200 mg/L-1	Hypertension	Hyperthyroidism
	Triglycerides < 150 mg/L-1	Diabetes	In diet
	Fasting glucose (plasma) < 100 mg/L-1	Smokers	Pregnant or lactating women
Normoglycemia	18.5 – 24.9	Cardiovascular disease	In medical treatment / supplements
BMI [kg/m2]	18 – 40	Secondary	Hepatic insufficiency

Abdominal circumference [cm].	Men < 90 Women < 80	hyperlipidemia Renal insufficiency	Infection / inflammatory disease (6 weeks prior to study)
Fat percentage [%] [cm]	Men < 19 Women < 33		
Systolic pressure [mmHg].	< 140		
Diastolic pressure [mmHg].	< 90		
Alcohol	Last consumption one week and a half		

The study adhered to the ethical principles for research on human subjects of the Declaration of Helsinki and was submitted to the ITESO Research Ethics Committee.

Acute Trial Clinical Intervention

An acute single-blind trial was conducted. Participants consumed a hibiscus-based drink (*H. sabdariffa*), or a 60ml placebo drink, and then received a Western-type diet characterized by excessive consumption of red meat, simple carbohydrates, ultra-processed products, colorants, saturated fats, refined sugars and very little intake of fiber and vitamins. After a washout period of more than 6 days, the participants underwent a second intervention with a different product from the first one (beverage to be evaluated or placebo, as appropriate), and the samples were repeated according to the following scheme

The protocol was previously explained to the volunteers and all those who give their written informed consent will be candidates to participate (Annex 1). On the day of the intervention, participants will arrive at 7 a.m., Mexico Central Time, with an overnight fast of 10-12h. They were requested a rest period of 30 min prior to blood pressure taking at the time of admission, in addition to the fact that they had to be seated, upright and with their feet on the floor during the process; the measurement was performed using a manometer on the left arm, elevated at the level of the heart (Gómez-León Mandujano et al., 2016).

Two types of sampling were performed:

(a) Urine.

For determination of phenolic compounds and organic acids in urine samples, a basal sample (T=0) was taken in a collection bottle. Once the hibiscus-based drink or placebo was ingested, samples were collected at the following times: 3h, 6h, 12h and 24h.

b) Blood

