For the studies of inflammation levels (IL-6 and TNF- α), and for the bioavailability of phenolic compounds and organic acids, blood samples were taken with the help of collecting tubes by venous puncture. Eight samples were taken, the first on arrival of the patients at basal time (T=B), then at 30 min (T=2), 1h (T=3), 1:30h (T=4), 2h (T=5), 3h (T=6), 4h (T=7) and 6h (T=8) after having ingested the hibiscus-based drink or the placebo.

In both interventions, patients received a Western diet (breakfast and lunch) characterized by excessive consumption of red meat, simple carbohydrates, ultra-processed products, dyes, saturated fats, refined sugars and very little intake of fiber and vitamins, adjusted to their physical characteristics, and supervised by a team of specialist nutritionists. The participants remained at the trial site without any type of physical exercise during the course of the study and in a relaxed environment with selected recreational activities; they also had a water fountain within their reach from which they could drink indefinitely and a team of medical services that was located at the trial site until its completion.

Sample handling.

For biochemical tests, plasma samples were separated by centrifugation at 3000 rpm for 10 minutes at 4 °C and divided into aliquots and stored at -20 °C until further analysis. On the other hand, urine samples were divided into aliquots and frozen at -20 °C until further analysis.

Extraction of phenolic metabolites and organic acids from biological samples.

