The inhibition of α -glucosidase of the beverages will be evaluated using the products of the different phases of the in vitro digestion and will follow the methodology described in the specifications of the α -glucosidase kit (Sigma-Aldrich #MAK123) where first 220 μ L of deionized water will be placed in a well of a reading plate and in another well 20 μ L of deionized water will be placed and 200 μ L of calibrator will be added to one of them. From the samples previously prepared in 50 mM phosphate buffer (pH 7.0) 20 μ L will be taken and placed in separate wells and 200 μ L of master solution will be transferred to each of them, the solution will be previously prepared with 200 μ L of p-nitrophenyl- α -D-glucopyranoside (NPG) buffer and 8 μ L of NPG substrate, then incubated at 37° C and absorbance will be measured at 405 nm using Synergy HT microplate reader

(Biotek Instruments, Inc., USA), the initial measurement (T-initial) will be read and after 20 minutes the final absorbance (T-final) will be taken.

The enzyme activity will be expressed in units per liter (unt/L) and calculated with the equation (Eq 6.2) where one enzyme unit is the amount of α -glucosidase that catalyzes the hydrolysis of 1 mM p -nitrophenyl- α -D-glucopyranoside per minute at pH 7.0.

$$\text{unt/L} = \frac{(\text{Abs final} - \text{Abs inicial})}{\text{Abs del calibrador} - \text{Abs del agua}} \times 250 \text{ unt/L} \quad \text{Ec 4.2}$$

Where:

Abs of the calibrator is the value for the calibrator at 20 minutes, Abs of the water represents the value of the water at 20 minutes and unt are units.

Evaluation of glycemic response.

To obtain the biological sample, a lancet will be used to puncture the thumb of the volunteer's finger and the sample will be collected on highly sensitive test strips for capillary glucose measurement of the OneTouch Ultra® System.

The portable system used for pre- and postprandial glucose measurement allows the monitoring of capillary glycemic response under experimental conditions for healthy subjects. With the use of this equipment, measurements will be obtained from t_0 (preprandial), and at 15, 30, 45, 60, 90 and 120 min (postprandial). The results will be expressed in mg/dL.

Insulin analysis.

Participants will be required to hold a hand warmer ($\sim 40^\circ\text{C}$) for 5 min before each capillary blood sampling, to stimulate peripheral blood flow.

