Blood samples (approx. 250 μL , 4-5 drops) will be drawn through finger pricks (OneTouch Ultra® lancets). Measurements over time will be similar to the glycemic response assessment technique. Samples will be placed in BD Microtainer SST tubes and kept at room temperature for 30 min. Samples will then be centrifuged

(5000 rpm, 25°C) for 10 min to obtain serum and kept in a freezer at -20 degrees Celsius until further analysis (Hossain et al., 2021).

Serum insulin concentrations will be analyzed using a two-site solid-phase enzyme immunoassay kit (Human Insulin ELISA Kit, Millipore, EZHI-14K), where the direct sandwich technique is used with two antibody solutions targeting insulin epitopes (Figure 6. 2) in such a way that the plate will be coated with a monoclonal antibody (capture) and then the sample will be added, so that the analyte of interest (insulin) will bind with the capture antibody and subsequently a horseradish peroxidase-labeled detection secondary antibody will be added, this antibody will bind to the antigens that will be in turn bound to the capture antibody, consequently will be added the substrate 3,3',5,5'- tetramethylbenzidine in buffer (TMB), forming a bluish coloration dependent on the insulin concentration, the reaction will be terminated by the addition of stop solution (HCl) obtaining as colored product (yellow) after acidification, which is quantifiable at 450 nm in a microplate reader (BioTek®, Synergy HT, Winooski, Vermont, USA). The results will be expressed in $\mu\text{U/L}$.

Statistical Analysis.

Statistical analysis: first stage

The normality of the data distribution will be evaluated by means of the Shapiro-Wilk test; if so, a Student's t-test will be used, or, on the contrary, a nonparametric Mann-Whitney test will be used to evaluate the statistical differences between the variables. The level of statistical significance will be a value of ($p < 0.05$). Statistical analysis will be performed with the STATISTICA program, version 10 (Statsoft.1984-2011 Inc., Tulsa, OK, USA).

Statistical analysis: second stage

Each sample will be considered as an experimental unit. Statistical analysis will be performed with the STATISTICA program, version 10 (Statsoft. 1984-2011 Inc., Tulsa, OK, USA). Differences in the response variables in the samples will be evaluated through a repeated-means ANOVA analysis. The level of statistical significance will be a value of ($p < 0.05$).

Calculation of the area under the curve.

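### The plan names a repeated-measures ANOVA for a 12-person crossover with no rule for missed samples or visits; run in its classical form, it would drop whole participants

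*Combined protocol and SAP*

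**What the plan says.** - **Size and design** (General Methodology, Participants; Acute Trial Clinical Intervention): "Twelve normo-weight volunteer participants without any medical condition were included". Each person is due to receive both drinks: "After a washout period of more than 6 days, the participants underwent a second intervention with a different product from the first one".
- **Capillary glucose** (Evaluation of glycemic response): one preprandial reading, "and at 15, 30, 45, 60, 90 and 120 min (postprandial", so seven times per visit.
- **Capillary insulin** (Insulin analysis): "Blood samples (approx. 250 μL , 4-5 drops) will be drawn through finger pricks". On timing, "Measurements over time will be similar to the glycemic response assessment technique", which I take as the same seven times.
- **Venous blood** (Acute Trial Clinical Intervention, Blood): "Eight samples were taken, the first on arrival of the patients at basal time", then seven more up to 6 h.
- **Urine** (same section): a basal sample and four later collections, the last at 24 h.
- **Analysis** (Statistical analysis: second stage): "Differences in the response variables in the samples will be evaluated through a repeated-means ANOVA analysis", in STATISTICA version 10 at the 5% level. The section also makes the sample, rather than the person, the experimental unit.

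The within-person factors are not named. The documents define no analysis set and no handling of missed samples, withdrawals or replacements. The AUC section has no rule for a missing time point.

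**The concern.** A classical repeated-measures ANOVA with drink and time within person needs a full row for each participant. One failed finger prick or unusable tube makes the row incomplete, and so does a missed second visit. The usual consequence is that all of that person's other values for the outcome are set aside.

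Each person is one twelfth (8.3%) of this trial, so small losses of samples can become sizeable losses of people. The analysed group could also differ from outcome to outcome. With no rule written beforehand, the handling would be chosen after the gaps are known.

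**Working it through.** The plan has no power, dropout or loss figure to reproduce, so what follows is illustration under stated assumptions.

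**1. Samples per person over two visits.** Glucose 7 × 2 = 14; insulin 14 if its times match glucose; venous 8 × 2 = 16; urine 5 × 2 = 10.

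**2. Expected complete participants.** With independent loss at rate m per sample and k samples, the expected number is 12 × (1 − m)^k.

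| Assumed loss m | Glucose or insulin (k = 14) | Venous (k = 16)* | Urine (k = 10)* |
|---|---|---|---|
| 1% | 10.4 | 10.2 | 10.9 |
| 2% | 9.0 | 8.7 | 9.8 |
| 3% | 7.8 | 7.4 | 8.8 |
| 5% | 5.9 | 5.3 | 7.2 |

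*Applies only if these outcomes are analysed by the same ANOVA.

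At 1% loss, the chance that at least one person has an incomplete glucose series is 1 − 0.99^(14 × 12) = 1 − 0.99^168 = 82%.

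**3. What one gap does.** In a simulated glucose data set of 12 × 2 × 7 = 168 values, one value was removed. A classical repeated-measures routine refused to run because the data were unbalanced. Deleting that participant leaves 11 × 14 = 154 values, so 167 − 154 = 13 observed values are discarded. A mixed model used all 167 values from 12 people. STATISTICA itself was not tested.

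**4. Precision.** A two-sided paired t-test at 5% serves as a stand-in for the drink contrast. The standardised difference detectable with 80% power is 0.89 at n = 12, 1.00 at n = 10 and 1.16 at n = 8.

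**5. Which mixed model is safe.** Suppose the person-by-visit SD and the residual SD are both 1, the data are complete (7 times, 12 people), the drinks are balanced over visits, and there is no drink effect.

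- True SE of the drink difference: √[2 × (1 + 1/7)/12] = 0.44.
- With a participant-only random effect, the person-by-visit variation is absorbed into the residual. After fixed effects for drink, visit, time and drink-by-time, 10 degrees of freedom have expected mean square 7 × 1 + 1 = 8, and 132 have expected mean square 1. The pooled residual variance is (10 × 8 + 132 × 1)/142 = 1.49.
- SE reported by that model: √[2 × 1.49/(7 × 12)] = 0.19.
- The true SE is 0.44/0.19 ≈ 2.3 times the reported one. A nominal 5% test then rejects with probability 2 × [1 − Φ(1.96/2.3)] ≈ 40%.

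Two simulations of this setting agree. The participant-only model rejected a true null 40% and 41% of the time, and a visit-adjusted paired analysis rejected 5.1% and 4.9%.

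**The case against.** The strongest reply is that the plan never says it will analyse complete participants only. That is right, and it limits the point.

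- **Unit of analysis.** Taken literally, making each sample the unit means that a missed draw costs one sample, not a person. That reading does not rescue the plan: it treats correlated samples from one person as independent, which conflicts with a repeated-measures analysis.
- **Which outcomes are covered.** In General Methodology, the First Stage heading stands above the participants, the crossover and the venous and urine sampling, and no second-stage heading follows. Cytokines and metabolites may therefore belong to the first-stage t-test or Mann-Whitney test. Neither needs a full 16-sample row, and the unpaired Mann-Whitney test would keep a one-visit participant. The ANOVA might even be meant for the in vitro digestion samples. A reader might infer that every human outcome shrinks to completers; the documents do not support that. Applying the ANOVA to glucose and insulin is itself a reading.
- **AUC.** A reader might infer that Eq 4.7 needs every increment, or that gaps would be entered as zero. As printed, the equation lists C among its terms but does not use it, and the text never mentions zero-filling. What stands is that no gap rule is given.
- **Loss rates.** They are assumed. Parts of the methods are in the past tense and report no losses, which shows neither that losses occurred nor that the data are complete. At 1% loss, the expected cost is fewer than two people.

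**Conclusion.** The concern holds conditionally. The plan names a repeated-measures ANOVA and has no rule for missed samples or visits. If drink and time are the within-person factors and the ANOVA is run classically, a participant with any gap leaves that outcome's analysis. For glucose or insulin, this leaves an expected 10.4 to 5.9 of 12 people over assumed losses of 1% to 5%.

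This rests on independent loss at one common rate, on insulin following the glucose times, and on these outcomes falling under the second stage. The stronger statement, that the plan restricts analysis to completers, is an inference from the method's name and should not be reported as the plan's rule.

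The point is still worth acting on: the sample is small, the gap in the plan is real, and the remedy is cheap. It should be corrected, but it does not show that any result is wrong.

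**What to change.** In the second-stage statistical section, for the human serial outcomes:

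1. Name the participant, not the sample, as the unit, and list the outcomes covered.
2. Replace the ANOVA with a linear mixed model fitted to every sample obtained, including those of one-visit participants. Use fixed effects for drink, visit, time and drink-by-time, and random effects for participant **and** participant-by-visit (or an equivalent within-visit covariance). Use Kenward-Roger or Satterthwaite degrees of freedom. Do not use a participant-only random effect for the serial values.
3. For AUC, use trapezoids over the actual sampling times. Bridge a single missing interior value from its neighbours; otherwise set the AUC to missing.
4. Report the number analysed for each drink and outcome.

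The cost is a few sentences and a mixed-model routine, with no extra participants or procedures. The downsides are slightly more complex modelling and a missing-at-random assumption: given the observed data, a missed sample is taken to be unrelated to its unseen value. Bridging across a missed peak would also understate that AUC somewhat.

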The glycemic and insulinemic values obtained experimentally will be recorded in a database. The area under the curve (AUC) will be calculated according to the equation proposed by Wolover and Jenkins (1986) (Eq.4.7.):

$$AUC = \left(\left(A + B + \frac{D}{2} \right) * 15 \right) + \left(\left(\frac{D}{2} + \frac{E}{2} \right) * 30 \right) + \left(\left(\frac{E^2 * 30}{2} \right) * (E + F) \right) \quad \text{Ec 4.7.}$$

Where A, B, C, D, E, F; represent the increase in glucose and insulin above baseline and 15 and 30 represent the time interval between blood samples. Any area below the fasting level will be discarded.

TECNOLÓGICO
NACIONAL DE MÉXICO

EXPECTED RESULTS

ITESO, Universidad
Jesuita de Guadalajara

This research aims to identify which metabolites are bioavailable in plasma and urine samples after ingestion of a hibiscus drink and to identify inflammation markers in the same normal-weight volunteers, as a potential adjuvant in the management of inflammation caused by COVID-19 disease, and generate a hypoglycemic effect by reducing the levels of glucose and serum insulin, consequent to the generation of possible modifications on the physiological mechanisms, including the inhibition of the activity of the α -amylase and α -glucosidase enzymes by the action of the bioactive compounds, as well as by the interaction with the rest of the ingredients that compose the beverage of interest.

- Abdel-Rahman, R. F., Hessin, A. F., Abdelbaset, M., Ogaly, H. A., Abd-Elsalam, R. M., & Hassan, S. M. (2017). Antihypertensive Effects of Roselle-Olive Combination in L-NAME-Induced Hypertensive Rats. *Oxidative Medicine and Cellular Longevity*, 2017. <https://doi.org/10.1155/2017/9460653>
- Abubakar, S. M., Ukeyima, M. T., Spencer, J. P. E., & Lovegrove, J. A. (2019). Acute effects of hibiscus sabdariffa calyces on postprandial blood pressure, vascular function, blood lipids, biomarkers of insulin resistance and inflammation in humans. *Nutrients*, 11(2). <https://doi.org/10.3390/nu11020341>

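### Eq 4.7 for the glucose and insulin AUC omits the 45-minute value and ends in a cubic term, so it is not an area and can reverse the treatment comparison

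*Combined protocol and SAP*

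**What the plan says.** Under Evaluation of glycemic response, capillary glucose is measured before the meal "and at 15, 30, 45, 60, 90 and 120 min (postprandial"), and "The results will be expressed in mg/dL". For insulin, the Insulin analysis section says: "Measurements over time will be similar to the glycemic response assessment technique".

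The section Calculation of the area under the curve then gives one equation, Eq 4.7, attributed to a published method:

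AUC = (A + B + D/2)×15 + (D/2 + E/2)×30 + (E²×30/2)×(E + F)

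The symbols are explained by "Where A, B, C, D, E, F; represent the increase in glucose and insulin above baseline", with the note that "15 and 30 represent the time interval between blood samples" and the rule "Any area below the fasting level will be discarded". No other AUC formula appears in the document.

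The equation serves specific objective 6, to evaluate the in vivo "GR and IR of the placebo beverage and treatment beverage". The sample is small: "Twelve normo-weight volunteer participants without any medical condition were included", each receiving both drinks.

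**The concern.** Six increments and six post-baseline times make A to F the values at 15, 30, 45, 60, 90 and 120 minutes. An area over that schedule must use all six, and every term must have the unit concentration × time. Eq 4.7 fails on both counts: C is defined but absent, and the last term multiplies a squared concentration by another concentration.

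If the equation is coded as printed, the 90- and 120-minute values dominate the result and the 45-minute sample has no influence. The answer also changes with the unit of measurement. A drink that lowers the response could then appear to raise it.

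**Working it through.** **Inputs.** Sampling times, interval widths and the glucose unit come from the sections cited above. The documents give no AUC value, glucose or insulin profile, or power calculation, so there is no stated figure to reproduce. All increments and variances below are assumptions.

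**Correct formula when all increments are positive:**

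(A + B + C + D/2)×15 + (D + E)/2×30 + (E + F)/2×30

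**Test 1: constant rise of 10 mg/dL.**
- Trapezoid: 35×15 + 300 + 300 = 1125.
- Eq 4.7: 25×15 + 300 + 1500×20 = 375 + 300 + 30000 = 30675, about 27 times too large.

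**Test 2: assumed placebo profile 20, 40, 35, 20, 10, 5 mg/dL.**
- Trapezoid: 105×15 + 450 + 225 = 2250.
- Eq 4.7: 70×15 + 450 + 1500×15 = 1050 + 450 + 22500 = 24000. This is 10.7 times too large, and the last term supplies 22500/24000 = 94%.
- Omitting C alone removes 35×15 = 525, or 23% of 2250.

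**Test 3: assumed hibiscus profile 10, 20, 17.5, 10, 12, 5 mg/dL.**
- Trapezoid: 52.5×15 + 330 + 255 = 1372.5, which is 39% below 2250.
- Eq 4.7: 35×15 + 330 + 2160×17 = 525 + 330 + 36720 = 37575, which is 57% above 24000. The direction is reversed.

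A second assumed pair behaves the same way. Placebo 20, 40, 35, 25, 10, 5 against active 12, 25, 22, 18, 12, 6 gives true areas of 2362.5 and 1740.0 (ratio 0.74); Eq 4.7 gives 24112.5 and 40020.0 (ratio 1.66).

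**Test 4: change of unit.** Dividing by 18 (an assumed conversion to mmol/L) divides the linear terms by 18 and the cubic term by 18³ = 5832.
- Placebo profile of test 2: 1500/18 + 22500/5832 = 87.2, against a true 2250/18 = 125 (0.70 times).
- Hibiscus profile of test 3: 855/18 + 36720/5832 = 53.8.

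The reversal seen in mg/dL is absent in mmol/L, so the direction depends on the unit. Insulin is to be reported in µU/L. For an assumed constant rise of 10,000 µU/L, the last term is 15×10⁸×(2×10⁴) = 3×10¹³, against a true area of 112.5×10⁴ = 1.125×10⁶.

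**Test 5: fall below baseline.** Take the placebo profile of test 2 with F = −15. Eq 4.7 gives 1050 + 450 + 1500×(−5) = −6000. With area below baseline discarded, the correct value is 1575 + 450 + 10²×30/(2×25) = 2085.

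**Test 6: simulation.** The setting was 12 participants in a crossover and a paired test at 0.05. Mean placebo increments were as in test 2, with lognormal between-person SD 0.30, visit SD 0.15, measurement SD 6 mg/dL and negatives set to 0.

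| True reduction | Power, correct area | Power, Eq 4.7 |
|---|---|---|
| 20% | 66–68% | 8–9% |
| 30% | 96% | 14–16% |

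The ranges cover repeated runs. A separate set of assumptions (SDs of 8–12 mg/dL by time point, 20% reduction) gave 61% and 6%. The mean difference then had the wrong sign in 0.7% of trials with the correct area and 29% with Eq 4.7.

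**Test 7: milder readings of the equation**, using the profiles of tests 2 and 3.

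| Reading | Placebo (true 2250) | Hibiscus (true 1372.5) |
|---|---|---|
| C missing, ordinary last trapezoid | 1725 (23% low) | 1110 |
| C missing, last term E²×30/(2(E+F)) | 1600 (29% low) | 982 |
| C restored, last term E²×30/(2(E+F)) | 2125 (6% low) | not needed here |

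The first two readings keep the right direction (hibiscus 36% and 39% lower), but none of the three returns the placebo area.

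**The case against.** The strongest reply is that the equation reached this review through a program reading a PDF. The product in the last term may have been a quotient on the page, and C may have been lost in reading. The large figures (10.7 times, the reversal, the unit dependence, the 9% power) all come from that last term. With only C missing, or with C missing and a quotient, the example does not reverse, and simulated power at a 20% reduction is 57–58% against 66%. This stands as a reason to check the source page and as a limit on the size of the harm. It does not rescue the formula: a triangle term fixed in the last interval is wrong whenever F is above baseline, as test 7 shows.

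The reversal also needs a particular shape, with a higher 90-minute value under the drink that has the smaller total area. Under a uniform 20% reduction without noise, Eq 4.7 keeps the right direction and exaggerates it: (1500×0.8 + 22500×0.512)/24000 = 0.53. Reversal is therefore possible, not certain.

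Two further points stand. The statistical sections do not name AUC as the tested variable, and an ANOVA on the individual time points would not be affected. They also do not say that the t-test is paired. On the same simulated data an unpaired test at a 20% reduction has 20% power with the correct area and 6% with Eq 4.7.

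Finally, the listed symbols, the interval widths and the rule on area below fasting suggest that an ordinary incremental trapezoid was intended. That makes the correction easy; it does not make the printed equation usable.

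**Conclusion.** The concern holds. As printed, Eq 4.7 ignores the 45-minute sample and adds a concentration-cubed term to concentration-by-time terms. Those two errors follow from the plan's own symbols and schedule and need no assumed data.

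The size of the effect does depend on assumed profiles. In mg/dL, the unit the plan sets for glucose, the examples are 10.7 to 27 times too large, and two assumed pairs of profiles reverse direction. Paired-test power at a 20% reduction falls from about two thirds to under 10%. These figures also require that the last term is as printed and that AUC is the quantity compared. Because AUC is the only summary defined for objective 6, the formula must be corrected before any AUC is calculated.

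**What to change.** Check Eq 4.7 against the source page, then replace it. When all increments are positive:

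AUC = (A + B + C + D/2)×15 + (D + E)×30/2 + (E + F)×30/2

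For any interval, not only the last, in which the curve crosses baseline, use the triangle above baseline: p²×h / (2×(p + n)). Here p is the positive increment, n the size of the fall below baseline and h the interval width. An interval lying wholly below baseline contributes zero, in line with the plan's rule.

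Verify the code on hand-worked profiles: a constant 10 mg/dL rise must return 1125, and 20, 40, 35, 20, 10, 5 must return 2250. The same text should say whether AUC is the variable compared between drinks.

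The cost is one equation and a short code check. No new samples or data are needed.
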